6.1 Study Design and Sample Size

This is an open-label study in which participants in 4 cohorts based on age and Schistosoma species of infection will receive a single treatment dose of the new L-PZQ ODT at Day 1. The study includes 2:1 randomization of children 4 to 6 years of age infected with *S. mansoni* to the PZQ ODT treatment (Treatment group 1a) or the control treatment (40 mg/Kg racemic PZQ crushed tablets, Treatment group 1b). Specifically,

- Cohort 1: *S. mansoni*-infected children 4 to 6 years of age (n=150) will be randomized in a 2:1 ratio. Treatment group 1a, n=100, will be treated with a single dose of 50 mg/Kg of L-PZQ ODT (as the test treatment); Treatment group 1b, n=50, will be treated with the reference PZQ commercial product (Biltricide® 600 mg) crushed tablets at a single dose of 40 mg/Kg (as the internal control treatment).
- Cohort 2: *S. mansoni*-infected children 2 to 3 years of age (n=30) will be treated with a single dose of 50 mg/Kg of L-PZQ ODT. The primary aim of the descriptive efficacy analysis in this cohort is to explore whether the treatment effect is consistent with the treatment effect in older children (not an independent proof of efficacy in this subgroup).
- Cohort 3: *S. mansoni*-infected infants and toddlers 3 to 24 months of age (n=25 to 65) will be treated with a single dose of 50 mg/Kg of L-PZQ ODT. The primary aim of the descriptive efficacy analysis in this cohort is to explore whether the treatment effect is

consistent with the treatment effect in older children (not an independent proof of efficacy in this subgroup).

- Cohort 4: *S. haematobium*-infected children 3 months to 6 years of age (n=60) will be treated with a single dose of 50 mg/Kg of L-PZQ ODT, to assess the safety and efficacy in this group (not an independent proof of efficacy in this subgroup). After 30 children are enrolled and treated in Cohort 4, the efficacy and safety data will be summarized and evaluated by the IDMC to decide whether there is a need to increase the dose to 60 mg/Kg.
¹ If a dose increase is needed, 30 additional patients will be added to this cohort (i.e., total sample size of 90 for Cohort 4, n=60 receiving the final dose) and treated with the 60 mg/Kg dose of L-PZQ ODT.
- ¹ An Independent Data Monitoring Committee (IDMC) meeting was held on the 09 March 2020 and a decision was made to increase the dose in Cohort 4 to 60 mg/kg.

6.2 Interim Efficacy and Safety Analysis

Independent Data Monitoring Committee (IDMC):

Cut-off for analysis: 30 participants are enrolled, treated, completed follow-up visit (17 to 21 days after treatment) and their data entered to the database, in Cohort 4.

Responsible party: Triclinium Clinical Development, Merck Healthcare KGaA.

An IDMC will evaluate the interim efficacy and safety results after 30 participants are enrolled and treated in Cohort 4, in order to determine whether there is a need to increase the dose of L-PZQ ODT to 60 mg/Kg in this Cohort. The IDMC will also review the safety data for all patients who have been treated with L-PZQ ODTs that are available at that time. The evaluation will be based on an extract from the on-going database as clean as possible. No database lock or soft lock is planned for this purpose.

Analysis results will be shared with the IDMC.

Interim Analysis:

Cut-off for analysis: The first 30 subjects in Cohort 4 treated with 60 mg/kg of L-PZQ ODT have completed all assessments.

Responsible party: Triclinium Clinical Development, Merck Healthcare KGaA.

An interim analysis for efficacy based on ongoing database without pausing the study is planned when the first 30 subjects in Cohort 4 treated with 60 mg/kg of L-PZQ ODT have completed all assessments. The results will be available only to the internal clinical team to inform other studies in the PZQ clinical program, e.g. whether another clinical trial is necessary to evaluate the efficacy of L-PZQ ODT on *S. haematobium* infected children. No action to this ongoing study is planned subsequent to the interim analysis. The evaluation will be based on an extract from the on-going database as clean as possible. No database lock or soft lock is planned for this purpose.

No hypothesis testing is planned, so no Type I error control is necessary.

6.3 Final Analysis

Cut-off for analysis: Final database lock.

Responsible party: Triclinium Clinical Development, Merck Healthcare KGaA.

Following completion of the trial, the final trial analyses identified in this IAP will be performed only after the last subject has completed the scheduled assessments of the trial with all trial data in-house, all data queries resolved, and the database locked.

All primary, secondary endpoints and safety endpoints will be analysed.

A data review meeting will be held prior to database lock. In addition, no database can be locked until this IAP has been approved.

7 Changes to the Planned Analyses in the Clinical Study Protocol

The statistical methods as described in the protocol and protocol amendments were adopted. There are no changes to the planned analyses.

Impact of COVID-19 considerations:

This is a single dose study with lean design. Efficacy assessments are taken at home based follow up visits. The impact of COVID-19 on efficacy assessment was deemed low. Missing data and increase in protocol deviations due to COVID-19 are not anticipated, hence no sample size re-estimation is planned, and no change in this IAP is made for COVID-19.

If in rare scenarios COVID-19 is diagnosed for any subjects, the occurrence of this disease will be summarized in the AE tables. If protocol deviation was determined with COVID-19 as the reason, the scenario will be also summarized in protocol deviation table(s).

8 Protocol Deviations and Analysis Populations

8.1 Definition of Protocol Deviations and Analysis Populations

Important protocol deviations are protocol deviations that might significantly affect the completeness, accuracy, and/or reliability of the study data or that might significantly affect a participant's rights, safety, or well-being.

Important protocol deviations include:

- Participants that are dosed on the study despite not satisfying the inclusion or meeting the exclusion criteria, i.e. any inclusion/exclusion criteria violations

- Participants that develop withdrawal criteria whilst on the study but are not withdrawn
- Participants that receive the wrong study intervention or an incorrect dose
- Deviation from Good Clinical Practice

The following deviations will be identified and confirmed prior to or at the Data Review Meeting at the latest:

- Subjects that receive any prohibited medications/foods/fluids as outlined in sections 5.3.1, 5.3.2, 6.5.2 and 6.5.3 of the protocol (see Appendix B for further guidance).
- Any missed doses of Investigational Medicinal Product (IMP)
- Vomiting within the first hour of IMP administration
- Any medical condition that may modify the pharmacokinetic profile of the IMP or compromise the natural immunity of the subject
- Stool and urine samples required for assessing any of the study endpoint are missing or collected out-of-window. Some of these important protocol deviations are clinically important, if leading to the exclusion of a participant from an analysis population (see Section 10.2)

Important protocol deviations should be documented in the SDTM DV dataset whether identified through sites monitoring, medical review or programming. A clinically-important protocol deviations need to be in listings and described in an appendix of the CSR.

8.2 Definition of Analysis Populations and Subgroups

Screening Analysis Population (SCR)

The Screening analysis population includes all participants who signed the informed consent.

Intention-to-Treat (ITT)

For the purposes of this trial the ITT analysis set described in the protocol and the safety analysis set described below are considered equivalent. For this reason, the safety analysis set will be utilized for ITT and safety analysis purposes.

Modified ITT Analysis Population (mITT)

The modified ITT (mITT) analysis population will include all enrolled participants who receive one dose of treatment and have baseline measurement. Children who require malaria treatment after enrollment in the study will not be included in the mITT population. The primary analysis of this study will be performed on the mITT population.

Per Protocol Analysis Population (PP)

Per-protocol (PP) Analysis population includes all participants who are in the mITT population and have one post baseline measurement for Cohorts 1, 2, 3 and 4a, and two post baseline measurements for Cohort 4b, without any clinically important protocol deviations. Details of the

criteria for exclusion from the PP population are provided below. An additional determination will be made prior to database lock, based on a review of data accrued during the conduct of the study.

Participants who meet any one of the following criteria will be excluded from the PP:

- Inclusion/exclusion violations
- Subjects that develop withdrawal criteria whilst on the study, but are not withdrawn
- Subjects that receive the incorrect treatment
- Subjects that receive any prohibited medications/foods/fluids as outlined in Sections 5.3, 6.5.2 and 6.5.3 of the protocol;
- Any missed doses of IMP
- Any medical condition that may modify the pharmacokinetic profile of the IMP or compromise the natural immunity of the subject
- End-of-study stool (C1-C3) samples or urine samples (C4) required for assessing the primary endpoint are missing or collected out-of-window

Safety Analysis Population (SAF)

The Safety analysis population will include all participants who receive a dose of study treatment. Participants will be analyzed according to the actual treatment they receive.

Pharmacokinetic Analysis Population (PKP)

The PK Analysis Population is a subset of the SAF population and will consist of all participants who receive at least one dose of active IMP and provide at least one measurable post-dose concentration. A measurement below lower limit of quantification (BLQ) is considered a valid measurement. Participants will be analyzed according to the actual treatment they received. Subjects in this analysis population may not have taken prohibited medications/foods/fluids, and may not have experienced any diarrhea or vomiting after IMP administration.

Additional Subgroup Analysis Populations

Subgroup analyses will be performed on subgroups as defined below.

The final parameterization will be updated and fixed at the Data Review Meeting at the latest and documented in an amendment to this IAP if different from the following definition.

The following subgroups will be defined:

- Age
 - 4 to 6 years of age (Cohorts 1 and 4)
 - 2 to 3 years of age (Cohorts 2 and 4)
 - 3 to < 24 months of age (Cohorts 3 and 4)
- Gender

- Male
- Female
- Severity of infection (as assessed at Pre-screening [D-28 to D-1])
 - *S. mansoni* infection
 - Light infection: 1 - 99 eggs per gram of faeces
 - Moderate/heavy infection: ≥ 100 eggs per gram of faeces
 - *S. haematobium* infection
 - Light infection: < 50 eggs/10 mL of urine
 - Heavy infection: ≥ 50 eggs/10 mL of urine
- Note: In summary tables, *S. haematobium* heavy infection will be classified as Moderate /Heavy when being presented side-to-side with other cohorts.
- Trial center/country
 - PPD
 - [REDACTED]

9 General Specifications for Data Analyses

Study intervention groups

Study intervention groups are defined and labelled as Biltricide® and L-PZQ ODT.

Unless otherwise indicated all analyses will be presented separately for treatment groups. Specifically, Cohorts 1a and 1b will be presented separately in all tables. In general, in this IAP the term “cohorts” represents Cohorts 1, 2, 3 and 4, whereas the term “treatment groups” stands for Cohorts 1a, 1b, 2, 3, 4a and 4b with 4a and 4b representing Cohort 4 participants treated with 50 mg/kg and 60 mg/kg, respectively.

Data handling after cut-off date

Data (other than the date of death and the date last known to be alive) obtained after the cut-off will not be displayed in any listings or used for summary statistics, e.g. laboratory values of samples taken after data cut-off, AEs with onset date after data cutoff, etc. will not be included in any analysis or listing.

Significance level

No formal comparisons were planned for the primary objective. [REDACTED]

[REDACTED]

Presentation of continuous and qualitative variables

Continuous variables will be summarized using descriptive statistics, i.e.

- number of participants, number of participants with missing values,
- mean, standard deviation,
- median, 25th percentile, 75th percentile (Q1, Q3),
- minimum and maximum.

Qualitative variables will be summarized by counts and percentages.

Unless otherwise stated, the calculation of proportions will be based on the number of participants of the analysis population of interest. Therefore, counts of missing observations will be included in the denominator and presented as a separate category.

The following conventions are applied for reporting descriptive statistics of all continuous:

| Statistic | Reporting convention |
|----------------|----------------------------|
| Mean | Observed + 1 decimal place |
| SD, SEM | Observed + 2 decimal place |
| Minimum | Observed |
| Median | Observed + 1 decimal place |
| Maximum | Observed |
| CV% | Up to 1 decimal place |
| Point Estimate | Observed + 1 decimal place |
| 95% CI | Observed + 1 decimal place |
| Q1 | Observed + 1 decimal place |
| Q3 | Observed + 1 decimal place |

Note: At rare situations, there might be deviations from the above convention.

Definition of baseline

In general, the last non-missing measurement prior to the study intervention administration will serve as the baseline measurement.

Definition of change from baseline

Change from baseline = visit value – baseline value

Percent Change from Baseline = $100 * (\text{visit value} - \text{baseline value}) / \text{baseline value}$

Note: If baseline observation is missing then respective subject summary will not be calculated for Change from Baseline or Percent Change from Baseline.

Definition of pre-treatment value

In general, the last non-missing measurement prior to the first study intervention will be used as the pre-treatment baseline measurement.

Definition of duration

If required, duration in days will be calculated by the difference of start and stop date + 1 (if not otherwise specified).

The time since an event will be calculated as reference date minus date of event.

Conversion factors

The following conversion factors will be used to convert days into months or years: 1 month = 30.4375 days, 1 year = 365.25 days.

Handling of missing data

Unless otherwise specified (Sections 13, 15, 16 and 17), missing data will not be imputed.

In all participant data listings, imputed values will be presented. In all listings imputed information will be flagged.

Missing statistics, e.g. when they cannot be calculated, should be presented as “ND”. For example, if n=1, the measure of variability (SD) cannot be computed and should be presented as “ND”.

Time window

Day 1 is the day of the study intervention, the day before is Day -1 (no Day 0 is defined).

Study day is defined relative to Day 1.

Software(s)

The statistical software SAS® (windows version 9.1 or higher) may be used to perform statistical analyses, produce tables, listings and figures and calculate summary statistics of PK Parameters if appropriate. WinNonlin (version 6.4 or higher) will be used for estimating PK parameters.

10 Study Participants

This section includes specifications for reporting participant disposition and study intervention/study discontinuations. Additionally, procedures for reporting protocol deviations are provided.

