## 6.6

### Dose Selection and Modification

This is an open-label study in which participants will receive a single treatment dose of the new L-PZQ ODT (Treatment group 1a, Cohorts 2, 3, and 4) or the commercial PZQ formulation (Treatment group 1b) at Day 1. Therefore, no dose modification is applicable.

If the participant vomits or spits the L-PZQ/Biltricide after dosing, he/she will not receive a new dose of L-PZQ/Biltricide. If vomiting occurs, water and/or food may be given at the Investigator's discretion and this will be documented in the CRF. Subjects will not be excluded from the analysis.

An IDMC will evaluate the interim safety and efficacy data after 30 participants are enrolled and treated in Cohort 4. The data will be summarized and evaluated to decide whether there is a need to increase the dose to 60 mg/kg in Cohort 4 (see Section 9.4.4).

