**Table 4** **PK parameters**

| Symbol           | Definition  |
|------------------|---|
| $C_{\max}$       | Maximum observed concentration in plasma  |
| $AUC_{0-t}$      | Area under the plasma concentration-time curve (AUC) from time zero to the last sampling time at which the concentration is at or above the lower limit of quantification |
| $t_{\max}$       | Time to reach the maximum plasma concentration  |
| $t_{\text{lag}}$ | Time prior to the first measurable (non zero) concentration   |

PK parameters will be evaluated and listed for all participants who provide sufficient concentration time data.

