16.1 Pharmacokinetics

To get information on systemic plasma concentrations after administration of L-PZQ ODT formulation in the targeted pediatric age groups, a subgroup of 20 participants 4 to 6 years of age (Treatment group 1a), 15 participants 2 to 3 years of age (Cohort 2), between 5 and 10 participants 3 to <24 months of age (Cohort 3), and 15 participants infected with *S. haematobium* (Cohort 4) are planned to supply blood samples for determination of systemic concentrations of R-Praziquantel, S-Praziquantel, R-4-OH-Trans Praziquantel and S-4-OH-Trans Praziquantel after treatment of L-PZQ 50 mg/kg. PK sampling from up to 15 participants in Treatment Group 1b will provide information on the systemic plasma concentrations

observed after Biltricide administration. An additional up to 15 participants will be collected for the 60 mg/kg dose group in Cohort 4b to study the systemic concentration of R-Praziquantel, S-Praziquantel, R-4-OH-Trans Praziquantel and S-4-OH-Trans Praziquantel after treatment of L-PZQ 60 mg/kg. A separate written informed consent will be obtained for PK sampling. Only participants with minimum hemoglobin of 10 g/dL will be asked to take part in the PK sub-study.

Blood samples of approximately 1 mL per time point will be collected for measurement of plasma concentrations of R-Praziquantel, S-Praziquantel, R-4-OH-Trans Praziquantel and S-4-OH-Trans Praziquantel, immediately prior to dosing (pre dose) and thereafter (post-dose), multiple times till 12 hours after dosing, as specified in the Schedule of Activities (Section 1.3 in protocol) and below. Instructions for the collection and handling of biological samples will be provided by the Sponsor. The actual date and time (24-hour clock time) of drug administration and each sample will be recorded in the eCRF.

Note: Analyses that took place prior to 01-Mar-2021 will only include R-Praziquantel and S-Praziquantel. All analyses taking place from 01-Mar-2021 will include 4 analytes R-Praziquantel, S-Praziquantel, R-4-OH-Trans Praziquantel and S-4-OH-Trans Praziquantel.

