16.1.1 Presentation of PK Concentration and PK Parameter Data

16.1.1.1 Listings and Tables (PK Analysis Population)

Statistical analyses and descriptive summaries of pharmacokinetic data will be performed on the PK Analysis Population (PKP, as defined in Section 8.2). The following PK tables and listings will be produced:

- a) Descriptive Statistics of PK Concentration Data:
 - PK measurements will be descriptively summarized using: number of non-missing observations (N), arithmetic mean (Mean), standard deviation (SD), coefficient of variation (CV%), minimum (Min), median (Median) and maximum (Max).
 - Descriptive statistics will only be calculated for N>2 in which a measurement of <LLOQ represents a valid measurement

- Descriptive statistics of PK concentration data will be calculated using values with the same precision as the source data and rounded for reporting purposes only.
- The following conventions will be applied when reporting descriptive statistics of PK concentration data:
 - Mean, Min, Median, Max: 3 significant digits
 - SD: 4 significant digits
 - CV%: 1 decimal place

b) Descriptive Statistics of PK Parameter Data

- PK parameter data will be descriptively summarized using: number of non-missing observations (as N), arithmetic mean, standard deviation (SD), coefficient of variation (CV%), minimum, median, maximum, geometric mean (GeoMean), the geometric coefficient of variation (GeoCV) and the 95% confidence interval for the GeoMean (LCI 95% GM, UCI 95% GM). For time to reach maximum observed concentration (t_{max}), only n, minimum, median, and maximum will be reported.
- Descriptive statistics will only be calculated for a PK parameter when $N > 2$.
- PK parameters read directly from the measurements (i.e. C_{max}) will be reported with the same precision as the source data. All other PK parameters will be reported to 3 significant figures. In export datasets, as well as in the SDTM PP domain, PK parameters will be provided with full precision and will not be rounded. Descriptive statistics of PK parameter data will be calculated using full precision values and rounded for reporting purposes only.
- The following conventions will be applied when reporting descriptive statistics of PK parameter data:
 - Mean, Min, Median, Max, GeoMean, 95% CI: 3 significant digits
 - SD: 4 significant digits
 - CV%, GeoCV%: 1 decimal place

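### SAP 8.2 removes from the PK population any child with vomiting or diarrhoea at any time after dosing, so an event after the last blood sample discards a complete profile

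*SAP*

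**What the plan says.** SAP 8.2 defines the PK population as treated children with at least one post-dose concentration. It then removes those who took prohibited medication, food or fluids, and adds that members "may not have experienced any diarrhea or vomiting after IMP administration". It gives no time limit and does not restrict the events to drug-related ones. SAP 16.1.1.1 makes this the only population for PK output: "Statistical analyses and descriptive summaries of pharmacokinetic data will be performed on the PK Analysis Population".

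Other passages point elsewhere:

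- Protocol 6.6: "If the participant vomits or spits the L-PZQ/Biltricide after dosing, he/she will not receive a new dose", and then "Subjects will not be excluded from the analysis".
- Protocol 8.5, below Table 4: "PK parameters will be evaluated and listed for all participants who provide sufficient concentration time data". SAP 16.1 repeats this sentence. Neither place carries a gastrointestinal exclusion.
- SAP 8.1 lists among the deviations to be confirmed by the Data Review Meeting "Vomiting within the first hour of IMP administration".
- SAP 7, on departures from the protocol: "There are no changes to the planned analyses".

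On timing, SAP 16.1 takes samples before dosing and then "multiple times till 12 hours after dosing". Protocol 8.3.1 captures adverse events up to the End-of-Study visit, Day 17 to 21.

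**The concern.** A child's Day 1 concentrations are fixed once the last sample is drawn. Diarrhoea on Day 10 cannot change them, yet under SAP 8.2 as written it removes that child from every PK table, listing and figure. Nothing in the rule separates such an event from vomiting minutes after the dose, where some of the drug may have been lost.

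The PK groups are small (5 to 20 children) and were sized on feasibility. In Cohort 3, with 5 to 10 sampled children, one lost child is 10% to 20% of the group. The passages also allow different datasets: a programmer following SAP 16.1 would keep children whom a programmer following SAP 8.2 would drop.

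**Working it through.** **1. Time windows.** Protocol Table 3 and SAP Table 1 put the last PK sample at 3 h (5 to <7 kg), 8 h (7 to <10 kg) or 12 h (10 kg and above). Adverse events are recorded to Day 17 to 21. Every vomiting or diarrhoea event between the last sample and that visit therefore triggers the exclusion without being able to affect the profile.

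**2. The passages side by side.**

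| Place | Vomiting | Diarrhoea | Time limit |
|---|---|---|---|
| SAP 8.2, PK population | excluded | excluded | none |
| Protocol 6.6 | not excluded | not mentioned | none |
| Protocol 8.5 and SAP 16.1 | no exclusion | no exclusion | not applicable |
| SAP 8.1, deviation | flagged | not mentioned | first hour |

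Protocol 6.6 conflicts with SAP 8.2 on vomiting only. The diarrhoea exclusion conflicts with protocol 8.5 and SAP 16.1. SAP 8.1 shows that a time-bounded criterion was available.

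**3. Size of the loss.** The plan states no precision or power for the PK subset, so there is no figure to reproduce.

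- Planned PK numbers (SAP 16.1): 1a 20, 1b up to 15, Cohort 2 15, Cohort 3 5 to 10, Cohort 4 at 50 mg/kg 15, Cohort 4 at 60 mg/kg up to 15. The total is 20 + 15 + 15 + (5 to 10) + 15 + 15 = 85 to 90.
- Phase II Part 1 (protocol 2.3): vomiting 11, diarrhoea 10, haemorrhagic diarrhoea 1, among 420 children. The counts follow a paragraph on drug-related events and are read here as drug-related. One event per child is assumed.
- q = (11 + 10 + 1)/420 = 22/420 = 5.2% (exact 95% CI 3.3% to 7.8%).
- Expected number lost = n × q:

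| Group size | Expected lost at 5.2% |
|---|---|
| 5 | 0.26 |
| 10 | 0.52 |
| 15 | 0.79 |
| 20 | 1.05 |
| 85 to 90 (all) | 4.5 to 4.7 |

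With vomiting alone (11/420 = 2.6%) the overall loss would be 2.2 to 2.4. At an assumed 10% it would be 8.5 to 9.0.

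**4. Direction of any bias.** Let r be mean exposure in excluded children divided by mean exposure in retained children. Then mean(retained)/mean(all) = 1/(1 − q + q·r). The documents do not give r, so a range is shown, at q = 5.2%:

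| r | Shift in mean exposure |
|---|---|
| 0.25 | +4.1% |
| 0.5 | +2.7% |
| 1 | 0% |
| 1.25 | −1.3% |
| 1.5 | −2.6% |

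For example, r = 0.5 gives 1/(1 − 0.0524 × 0.5) = 1.027. The sign depends wholly on r.

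**5. Visibility.** SAP 10.1 counts children in the mITT, PP, screening and safety populations, and SAP 10.2.2 gives exclusion reasons for mITT and PP only. Neither covers the PK population, so neither would show how many children were dropped from it or why.

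**The case against.** The strongest defence is that the SAP was entitled to define this population. Protocol Table 6 has no PK population, and protocol 9.4.3 leaves PK detail to the analysis plan. Protocol 6.6 does not name PK or mention diarrhoea, and the mITT and PP definitions in SAP 8.2 do not list vomiting as a reason for exclusion. Leaving early vomiters out of an exposure summary can be reasonable, because it describes exposure when the dose is retained. PK is secondary and descriptive. In a group of 5 to 10, one child who lost the dose could distort the mean.

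Most of this stands. It supports a PK-specific exclusion for events that could have altered the profile. It does not support one that runs for weeks after sampling ends, or the unreconciled conflict with protocol 8.5 and SAP 16.1.

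The Phase II rate is also a poor measure of the avoidable loss. Protocol 6.9 expects drug-related events within about 12 hours, so the 5.2% is probably mostly in-window. The counts pool several formulations and doses. L-PZQ ODT 45 mg/kg had 2 participants with related events, while the 60 mg/kg arm had 12 such events. In the other direction, the exclusion counts events of any cause, for which no rate is given.

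A reader might infer that the rule inflates reported exposure because early vomiters have low concentrations. The documents do not show this. They give no exposure data by event status, protocol 8.2 says undesirable effects depend on dosage (so affected children could have higher exposure), and late events imply no direction.

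**Conclusion.** The point holds as a minor one. The PK exclusion in SAP 8.2 is unbounded in time. Followed as written, it can discard complete profiles that the event could not have affected. It conflicts with protocol 6.6 for vomiting and with protocol 8.5 and SAP 16.1 for both events, is out of line with the first-hour criterion in SAP 8.1, and is not declared in SAP 7.

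The expected loss is about 0.8 of 15 or 1 of 20 children per group, 4.5 to 4.7 of 85 to 90 overall. This assumes that the Phase II drug-related rate carries over with one event per child. How much of that loss falls after the last sample cannot be derived from the documents, and late events of any cause would add to it.

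Two stronger readings are not supported. One is that mean exposure is overstated: the shift at the Phase II rate runs from +4.1% to −2.6% over the assumed range of r. The other is that protocol 6.6 obliges the main PK table to keep every affected child: that section covers vomiting and spitting only, and whether to include in-window events is partly a choice of what the summary should describe.

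**What to change.** Reconcile SAP 8.2 with protocol 6.6 and 8.5 and with SAP 8.1 and 16.1, and record any remaining departure from the protocol in SAP 7. Specifically:

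1. Do not exclude a child from PK for vomiting or diarrhoea that starts after that child's own last PK sample.
2. Flag events that start between dosing and the last sample, and present the PK summaries both with and without those children. State how an event with a missing onset time on the dosing day is classed. SAP 15.1 would set it to the dosing time, which places it in the window.
3. Keep the exclusion for prohibited medication, food and fluids unchanged.
4. Add the PK population to the disposition counts in SAP 10.1 and to the exclusion reasons in SAP 10.2.2.

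The cost is a few lines of SAP text and one extra table. The summary that includes children with in-window events will be somewhat more variable, most visibly in Cohort 3.
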